8.2. SAFETY ASSESSMENTS

As noted, this study is considered minimal risk. That said, the following safety procedures are included as part of this protocol.

- Patients with advanced chronic kidney disease are at increased risk for high blood potassium levels. This risk may be increased by a dietary pattern high in potassium, specifically a pattern with high fruit and vegetable intake, as advocated by our intervention. To reduce this risk, potential participants with advanced renal disease are excluded from this study, as follows:
 - As outlined in Section 5.5, participants screened for the study for whom we can calculate an eGFR based on a previously measured creatinine are excluded if the eGFR < 30 mL/min/1.73 m².
 - As outlined in Section 5.4, among participants referred to the study who have not had a creatinine and thus a calculated eGFR as part of their clinical care during the prior 2 years, we will assess creatinine and eGFR as part of the baseline lab work and potential participants will be excluded if eGFR < 30 mL/min/1.73 m².
- As part of the physical activity intervention, an information sheet on safety while being active will be given to participants in the intervention group.
- If a participant loses more than 35 pounds at the 4 month follow-up, 80 pounds at 12 month follow-up, or 100 pounds at 24 month follow-up, their study record and the EHR will be reviewed by [name] in conjunction with the participant's PCP to determine if additional evaluation is warranted for underlying medical disease that may be contributing to weight loss.

Addendum 7/25/21 to address high LDL cholesterol (> 190 mg/dL): In addition to uploading LabCorp lab report to Epic with CC copy to PCP (which goes to the Epic in box folder "Media Manager"), will also send Epic staff message to PCP noting LDL >190 if no entry in the chart indicating high LDL already

addressed (most commonly this will be due to statin intolerance). Rationale for sending “staff message” is that this Epic inbox is likely to be reviewed more frequently than “Media Manager.”

8.3 ADVERSE EVENTS AND SERIOUS ADVERSE EVENTS

8.3.1 DEFINITION OF ADVERSE EVENTS

This protocol uses the definition of adverse event from 21 CFR 312.32 (a): any untoward medical occurrence associated with the use of an intervention in humans, ***whether or not considered intervention-related.***

8.3.2 DEFINITION OF SERIOUS ADVERSE EVENTS

For this study a serious adverse event includes, as outlined at: <https://www.hhs.gov/ohrp/regulations-and-policy/guidance/reviewing-unanticipated-problems/index.html>:

1. results in death;
2. is life-threatening (places the subject at immediate risk of death from the event as it occurred);
3. results in inpatient hospitalization or prolongation of existing hospitalization;
4. results in a persistent or significant disability/incapacity;
5. results in a congenital anomaly/birth defect; or
6. based upon appropriate medical judgment, may jeopardize the subject’s health and may require medical or surgical intervention to prevent one of the other outcomes listed in this definition (examples of such events include allergic bronchospasm requiring intensive treatment in the emergency room or at home, blood dyscrasias or convulsions that do not result in inpatient hospitalization, or the development of drug dependency or drug abuse)

8.3.3 CLASSIFICATION OF AN ADVERSE EVENT

8.3.3.1 SEVERITY OF EVENT

For adverse events (AEs) not included in the protocol defined grading system, the following guidelines will be used to describe severity.

- **Mild** – Events require minimal or no treatment and do not interfere with the participant’s daily activities.
- **Moderate** – Events result in a low level of inconvenience or concern with the therapeutic measures. Moderate events may cause some interference with functioning.
- **Severe** – Events interrupt a participant’s usual daily activity and may require systemic drug therapy or other treatment. Severe events are usually potentially life-threatening or incapacitating. Of note, the term “severe” does not necessarily equate to “serious”.

8.3.3.2 RELATIONSHIP TO STUDY INTERVENTION/EXPERIMENTAL MANIPULATION

All adverse events (AEs) will have their relationship to study procedures, including the intervention, assessed by an appropriately-trained clinician based on temporal relationship and his/her clinical judgment. The degree of certainty about causality will be graded using the categories below.

- **Definitely Related** – There is clear evidence to suggest a causal relationship, and other possible contributing factors can be ruled out. The clinical event, including an abnormal laboratory test result, occurs in a plausible time relationship to study procedures administration and cannot be explained by concurrent disease or other drugs or chemicals. The response to withdrawal of the study procedures should be clinically plausible. The event must be pharmacologically or phenomenologically definitive.
- **Probably Related** – There is evidence to suggest a causal relationship, and the influence of other factors is unlikely. The clinical event, including an abnormal laboratory test result, occurs within a reasonable time after administration of the study procedures, is unlikely to be attributed to concurrent disease or other drugs or chemicals, and follows a clinically reasonable response on withdrawal.
- **Potentially Related** – There is some evidence to suggest a causal relationship (e.g., the event occurred within a reasonable time after administration of study procedures). However, other factors may have contributed to the event (e.g., the participant’s clinical condition, other concomitant events). Although an AE may rate only as “possibly related” soon after discovery, it can be flagged as requiring more information and later be upgraded to “probably related” or “definitely related”, as appropriate.
- **Unlikely to be related** – A clinical event, including an abnormal laboratory test result, whose temporal relationship to study procedures administration makes a causal relationship improbable (e.g., the event did not occur within a reasonable time after administration of the study procedures) and in which other drugs or chemicals or underlying disease provides plausible explanations (e.g., the participant’s clinical condition, other concomitant treatments).
- **Not Related** – The AE is completely independent of study procedures administration, and/or evidence exists that the event is definitely related to another etiology. There must be an alternative, definitive etiology documented by the clinician.

8.3.3.3 EXPECTEDNESS

Drs. [name] and [name] will be responsible for determining whether an adverse event (AE) is expected or unexpected. An AE will be considered unexpected if the nature, severity, or frequency of the event is not consistent with the risk information previously described for the study procedures.

8.3.4 TIME PERIOD AND FREQUENCY FOR EVENT ASSESSMENT AND FOLLOW-UP

Solicited potential adverse events will occur at each follow-up measurement visit (4, 12, and 24 months). They include the following and we will ask if evaluation for these events included emergency room visit or overnight hospital stay.

- Acute myocardial infarction
- Angina pectoris
- Stroke
 - Thrombotic
 - Hemorrhagic
- TIA
- Heart failure
- Coronary bypass surgery
- Cancer
 - Type of cancer
- Broken bone
 - Type of fracture
- Light headedness or dizziness
- Pneumonia
- Other infection
 - UTI
 - Other
- Hypoglycemia
 - Other

As allowed by our HIPAA authorization, the EHR will be reviewed to confirm the above events and modify the date of occurrence if not accurately provided by the participant. For clinical events that were managed outside of facilities with EHR data available to investigators, we will request that participants sign a release of medical information so that pertinent medical records can be reviewed.

Unsolicited adverse events (AE) or serious adverse events (SAE) may come to the attention of study staff during counseling visits, phone calls, or via other channels of communications. They will be categorized as above and entered into the appropriate follow-up questionnaire at the time of occurrence.

Information to be collected about AEs and SAEs includes event description, time of onset, study clinician's assessment of severity, relationship to study procedures (assessed only by those with the training and authority to make a diagnosis), and time of resolution/stabilization of the event. All AEs occurring while on study will be documented appropriately regardless of relationship. All AEs will be followed to adequate resolution.

Any medical or psychiatric condition that is present at the time that the participant is screened will be considered as baseline and not reported as an AE. However, if the study participant's condition deteriorates at any time during the study, it will be recorded as an AE.

Changes in the severity of an AE will be documented to allow an assessment of the duration of the event at each level of severity to be performed. Documentation of onset and duration of each episode will be maintained for AEs characterized as intermittent.

Study staff will record events with start dates occurring any time after informed consent is obtained until the last day of study participation.

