## **6.5 Per Protocol Population**

The Per Protocol Population for assessment of weight change at 24 months will be a subset of the ITT population and will exclude participants who did not adequately adhere to the protocol as defined below for their assigned treatment arm, for whatever reason, and did not attend the final measurement visit.

Specifications to be included in per protocol analysis.

Both study groups.

- Measurement visits: attends the final measurement visit

Group 1: Med-South (Phase 1 = 4 months; Phase 2 = 8 months; Phase 3 = 12 months. There were 30 planned visits over 24 months; 75% would be 22 visits total; 75% of each = approximately 3, 10, 9, respectively.)

- **Phase 1** -- 4 major counseling sessions: attended at least 3 visits
- **Phase 2** -- 14 sessions planned (8 weekly → 6 monthly; optional brief follow-up): attended at least 10 visits.
- **Phase 3** -- 12 sessions planned (monthly; optional brief follow-up): attended at least 9 visits.

Group 2 WW

- As of 9/10/24, we have not received data from WW, though we are expected to receive these data. When available we will operationalize definition akin to 75% engagement of group 1.

We will also assess per protocol outcomes at 4 and 12 months for those meeting definitions as above and will follow-up data at these time points respectively.

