## **9.5 Safety and Tolerability Analyses**

Prior to analysis, any data-captured adverse events will be coded by the principal investigators. Each type of event (by seriousness, severity, relationship to study) will be descriptively summarized in frequency tables by group (including only a single occurrence of any distinct type of event for any participant). The number of CVD events, ER visits, and hospitalizations will also be descriptively summarized by group. No inferential statistics (p-values or confidence intervals) are planned for comparing safety data between groups.

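### By-arm adverse event tables mix unequal ascertainment: counselling gives Med-South alone an extra scheduled route for non-serious or poorly recalled events to be recorded.

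*Protocol*

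**What the plan says.** **Common route.** Protocol 8.3.4 solicits one list of events at the 4, 12 and 24 month visits in both arms. Protocol 8.1.4 adds emergency visits and hospital admissions at every follow-up questionnaire.

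**Second route.** Protocol 8.3.4 says unsolicited events "may come to the attention of study staff during counseling visits, phone calls, or via other channels of communications". They take the same categories as the solicited events and are "entered into the appropriate follow-up questionnaire at the time of occurrence". The items to be recorded for each event cover description, onset, severity, relationship and resolution. How the event became known is not among them.

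**Who has counselling.** SAP 6.5, for Med-South: "There were 30 planned visits over 24 months; 75% would be 22 visits total". Protocol 6.1.2 adds a call about a week after each Phase I session and 6-12 calls in Phase II. For WW, Protocol 6.1.1 says staff will not actively promote participation after start-up. Protocol 6.2.1 lists what WW will supply, and adverse events are not on the list.

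**Reporting.** Under Protocol 9.4.4 and SAP 9.5, events are "descriptively summarized in frequency tables by group". Each event type is counted once per participant and no inference is made. Neither document splits the tables by source or comments on unequal ascertainment.

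**The concern.** A by-arm table compares arms even without p-values. If one arm has many more scheduled conversations with study staff, and whatever is mentioned there enters the same table, a difference in frequency can arise from detection alone.

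Two audiences would read such a difference. Protocol 6.3 says the reports to the monitoring committee contain unblinded data, and the committee's charter (Protocol 10.1.6) has it review adverse events for evidence of harm. Readers of the trial report would see the same by-arm frequencies. The primary endpoint is not touched.

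**Working it through.** **1. The plan's session count.** SAP 6.5 gives Phase 1 as "4 major counseling sessions: attended at least 3 visits", Phase 2 as "14 sessions planned" and Phase 3 as "12 sessions planned (monthly; optional brief follow-up): attended at least 9 visits".
- Planned sessions: 4 + 14 + 12 = 30, as stated.
- The 75% threshold: 0.75 × 30 = 22.5, and the phase minima sum to 3 + 10 + 9 = 22, as stated.
- With about 4 Phase I calls and 6-12 Phase II calls: 30 + 4 + 6 = 40 to 30 + 4 + 12 = 46 planned Med-South counselling contacts. WW has no scheduled counterpart with study staff.

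**2. Do the existing safeguards equalise the arms?**
- *Record review.* In Protocol 8.1.4 it follows a positive participant report; in 8.3.4 it confirms events. It does not look for events that a WW participant failed to mention.
- *Counting each type once.* This removes repeats of an event heard in counselling and reported again at a visit. It does not remove an event type that surfaced only in counselling.
- *Recall.* Nominal gaps between visits are 4, 8 and 12 months, and the allowed windows can lengthen them. The solicited list includes dizziness, hypoglycemia and minor infection, which are easier to forget than a stroke or an admission.

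**3. Size under a simple model.** Assume the same true risk in both arms. Visits capture a fraction v of affected participants in each arm. Counselling captures a fraction u of those the visits miss, in Med-South only. The observed Med-South:WW risk ratio is

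R = [v + (1 − v)u] / v

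Neither v nor u is in the documents; both are assumed.

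| v | u = 0.25 | u = 0.50 |
|---|---|---|
| 1.0 | 1.00 | 1.00 |
| 0.9 | 0.925/0.9 = 1.03 | 0.95/0.9 = 1.06 |
| 0.7 | 0.775/0.7 = 1.11 | 0.85/0.7 = 1.21 |
| 0.6 | 0.70/0.6 = 1.17 | 0.80/0.6 = 1.33 |

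Illustration with 180 per arm, an assumed true risk of 40%, v = 0.7 and u = 0.5:
- WW shows 180 × 0.4 × 0.7 = 50.4 participants with an event.
- Med-South shows 180 × 0.4 × 0.85 = 61.2.
- The gap is 10.8/180 = 6 percentage points, from detection alone.

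**4. After the fix.** In a table of visit-elicited events only, both arms have three ascertainment points. With equal true risk and equal visit capture, R = v/v = 1.00.

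**The case against.** A reader might infer that the tables will overstate harm in Med-South. The documents do not support that. Events heard in counselling are real; WW is the arm that is under-detected, and only for events its participants never report at a visit. Infarction, stroke, cancer, fracture, emergency visits and admissions are asked about identically in both arms and counted once per type. This narrows the problem to non-serious or poorly recalled events.

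A reader might also set 30 + 3 = 33 contacts against 3 and treat that as a detection ratio. It is not one. Protocol 6.1.2 places the first Phase II session at the 4-month data collection visit, so some occasions would be counted twice. Phase III calls were given as needed, and the listed session content contains no adverse event question. Nor is it supported that WW participants have no study contact between visits: phone calls and other channels are open to both arms, and Protocol 5.5 provides for contacting anyone who is late. The model sets this WW capture to zero, so it leans towards a larger ratio.

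The tables are descriptive and split by seriousness, severity and relationship, so an excess of mild, unrelated events would be visible as such. That limits the consequence. It does not show whether such an excess came from detection.

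Finally, a comparison restricted to visit-solicited, record-confirmed events would do damage. A participant who dies cannot be asked at a visit. Protocol 7.1 stops follow-up measures at withdrawal, Protocol 7.2 makes a new cancer a reason for withdrawal, and dizziness that never reached a clinician cannot be confirmed. This objection stands in full and shapes the fix.

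**Conclusion.** The concern holds in limited form. Following the plan produces by-group tables with unequal ascertainment. The likely direction is a higher apparent event frequency in Med-South relative to WW, mainly for non-serious or poorly recalled events; major events asked about at visits should be little affected.

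The size cannot be derived from the documents. With equal true risk the ratio is 1.00 if visits capture everything, and about 1.03 to 1.33 if visits capture 60-90% and counselling captures 25-50% of the remainder. The range rests on those assumed fractions, on equal recall at visits in both arms, and on no off-visit capture in WW. It shows what the mechanism could do and does not predict this trial's result.

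**What to change.** - Record the source of first detection for each event: visit-solicited, or counselling/other unsolicited. Where needed, assign it from event entry dates and the counselling session dates that Protocol 6.2.1 has logged in REDCap.
- Keep the full by-arm table of all events, including all deaths, serious events and events before withdrawal.
- Add a by-arm table limited to events elicited at the three common visits, as the like-for-like comparison of non-serious events. An event already heard in counselling should be asked about again at the visit and counted if reported there; dropping every such event would tilt the table the other way.
- Do not require record confirmation for inclusion.
- Add a note to both tables that ascertainment between visits was unequal.

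**Cost.** One field, some retrospective classification and one extra table. The SAP was drafted on 9/10/24, after randomization was complete, and already cites the observed median 24-month follow-up, so much of the classification would be retrospective. Where the form cannot show whether an event first heard in counselling was also reported at a visit, the added table should say so and be shown with and without those events.

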8.3.5 ADVERSE EVENT REPORTING

Adverse events will be reported as follows:

SAEs that include the following and are 1) definitely, 2) probably, or 3) potentially related to the study will be reported to the chair of the DSMC and IRB within 1 working day:

- Results in death
- Is life-threatening (places the subject at immediate risk of death from the event as it occurred)

Other SAEs and AEs will be reported to the Chair of the DSMC (by the 15th of each month for the preceding month) and will be summarized for review at each meeting of the DSMC.

Reports of adverse events to the UNC IRB will follow their policy as outlined below:

1. Do not wait to submit a reportable event to the IRB until you have all the information about the event. Report the event promptly and follow-up with additional information as it becomes available.
2. A UPIRSO (Unanticipated Problem Involving Risks to Subjects or Others) that is also a Serious Adverse Event must be reported ASAP, but no later than one (1) week from the time you become aware of the event.
3. All other UPIRSOs must be reported ASAP, but no later than two (2) weeks from the time you become aware of the event.

8.3.6 SERIOUS ADVERSE EVENT REPORTING

As outlined above in Section 8.3.5

8.3.7 REPORTING EVENTS TO PARTICIPANTS

Participants will be aware of events we consider AEs and SAEs as they will be reported to us by participants. Given the low risk nature of this study, we do not anticipate reporting summary information on adverse events to participants. The only “incidental finding” from the lab work reported to patients and PCPs would be an unexpected elevation in CRP. We will instruct the PCP to respond to this type of findings as they would see as appropriate. We do not consider elevations in blood lipids and A1c to be incidental as they likely reflect an underlying biologic process that PCPs are familiar with and able to respond to in an appropriate fashion.

8.38 EVENTS OF SPECIAL INTEREST

N/A.

8.3.9 REPORTING OF PREGNANCY

Pregnancy: Study participants who become pregnant may continue to participate in the study with the understanding that weight loss goals will be suspended during pregnancy through 3 months postpartum. If a pregnant participant wishes to continue with counseling sessions during pregnancy, the focus on counseling will be on dietary quality. The participant may resume full participation 3 months postpartum. Any data collected while the participant is pregnant will be censored and follow-up data will not be collected until the participant is 6 months postpartum.

8.4 UNANTICIPATED PROBLEMS

8.4.1 DEFINITION OF UNANTICIPATED PROBLEMS

This protocol uses the definition of Unanticipated Problems as defined by the Office for Human Research Protections (OHRP). OHRP considers unanticipated problems involving risks to participants or others to include, in general, any incident, experience, or outcome that meets all of the following criteria:

- Unexpected in terms of nature, severity, or frequency given (a) the research procedures that are described in the protocol-related documents, such as the Institutional Review Board (IRB)-approved research protocol and informed consent document; and (b) the characteristics of the participant population being studied;
- Related or possibly related to participation in the research (“possibly related” means there is a reasonable possibility that the incident, experience, or outcome may have been caused by the procedures involved in the research); and
- Suggests that the research places participants or others at a greater risk of harm (including physical, psychological, economic, or social harm) than was previously known or recognized.

8.4.2 UNANTICIPATED PROBLEMS REPORTING

The investigator will report unanticipated problems (UPs) to the reviewing Institutional Review Board (IRB) and to the DSMC. The UP report will include the following information:

- Protocol identifying information: protocol title and number, PI's name, and the IRB project number
- A detailed description of the event, incident, experience, or outcome
- An explanation of the basis for determining that the event, incident, experience, or outcome represents an UP
- A description of any changes to the protocol or other corrective actions that have been taken or are proposed in response to the UP

To satisfy the requirement for prompt reporting, UPs will be reported using the following timeline:

- UPs that are serious adverse events (SAEs) will be reported to the IRB and to the DSMC ASAP but no later than one week of when the investigator becoming aware of the event.
- Any other UP will be reported to the IRB and to DSMC ASAP but not later than within 2 weeks of the investigator becoming aware of the problem

